## PROTOCOL

Neurosteroids as Novel Therapeutic Agents for PTSD in OEF/OIF/OND Veterans  
PI: [name], PhD

senior author on these pivotal trials and is a collaborator (please see accompanying letter) along with [name] who was a co-investigator and is the primary mentor for the CDA. Subsequent testing with functionally defined ROIs will be used to make statistical inferences about treatment response and to identify correlations with cognitive changes, CAPS-5 scores, and neurosteroid levels. In addition, we propose to study the correlation between PTSD symptom severity and disruption in fear systems interrogated by the task paradigms. This will be probed further by examining correlation between the hypothesized clinical behaviors and fear system activation during the associated task (e.g., severity of hypervigilance symptoms and activation. Correction for the family-wise error rate will be based upon the Gaussian random field (GRF) theory that is implemented in FSL (Worsley et al., 1996).

Primary outcome analyses will be based on maps of activation, reaction time, and on-line accuracy judgments via a 2 (drug type: DHEA or Placebo)  $\times$  3 (face type: angry, fearful, neutral)  $\times$  3 (condition: male/female, inside/outside, like/dislike) repeated-measures ANOVA for main effects and interactions. Follow-up effect analyses will be performed with two-tailed *t*-tests and significance threshold at 0.05 with correction for multiple comparisons. Z-score images from the individual activation maps will be entered in second-level random-effects analyses using SPM8 and corrected for multiple comparisons,  $p<0.05$ . Activation threshold and cluster size will be determined using AlphaSim (Ward, 2000) to correspond to a false-positive rate of  $p<0.05$ , corrected for multiple comparisons within ROIs. Voxel coordinates that will be reported will correspond to standardized MNI space. The time series from significant clusters within regions of group difference will be used in a psychophysiological interaction (PPI) analysis. Deconvolved time series in the anatomical right amygdala will be extracted for each subject and represent the first regressor in the PPI analysis (physiological variable). The experimental condition is the second regressor (emotion processing; psychological variable). The regressor of interest will be the interaction between the time series of the seed region and the experimental condition.

Secondary outcome analyses will be based on a repeated measures ANOVA approach modeling difference-from-baseline scores at Weeks 2, 4, 6, and 8. These time-dependent outcomes will be estimated using a class of statistical models variously referred to as hierarchical linear models (HLM), linear mixed-models, (LMM) or multilevel models. Within this approach, each individual's measurements over time are initially modeled as an individual growth trajectory plus an error term. The individual trajectories are subsequently modeled as a function of differences between individuals on covariates of interest (e.g., treatment proxies, etc.). These models extend traditional approaches for modeling longitudinal data (e.g., time-series analyses or repeated measures ANOVAs) by allowing for missing values, covariance structures other than compound symmetry (e.g. unstructured typically is a first option), varied measurement intervals, and likelihood estimates based on all available (outcome) data. These procedures are be implemented in SAS v9.4 using PROC MIXED for normally distributed data and GLIMMIX for non-normally distributed data. The latter can estimate a variety of categorical outcomes including Poisson and binomial distributions.

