### Design

This is a parallel-group, double-blind, placebo (PBO)-controlled, randomized Phase 2 pilot study using adjunctive dehydroxyepiandrosterone [DHEA (400 mg)] will be evaluated to establish Proof of Concept (POC) for this agent in OEF/OIF/OND Veterans with PTSD.

Aim 1. To determine the effects of an acute oral administration of adjunctive DHEA (400 mg) on neuroimaging measures of functional connectivity. We will conduct a parallel-group, double-blind, placebo (PBO)-controlled, randomized Phase 2 pilot study with one-time oral DHEA 400 mg in target engagement. To establish POC, we seek to determine if DHEA is superior to PBO in target engagement of neural circuits related to fear-anxiety-emotion regulation using the shifted-attention emotion appraisal (SEAT) paradigm (see below). Following a two-week placebo lead-in period (all participants), subjects will be randomized to receive a one-time oral dose of adjunctive DHEA (400mg) or PBO. Neuroimaging will occur 2 hours following drug administration for peak level effects on target engagement of fear-anxiety emotion circuit connectivity, as previously conducted by Sripada, [name], [name] et al.).

Primary Outcome Measure The primary outcome measure will be functional connectivity between amygdala-hippocampus assessed using fMRI based SEAT Paradigm as a target engagement endpoint. The fMRI based SEAT Paradigm has been previously validated to an acute administration of DHEA (400 mg) in healthy volunteers by members of my career development team, Drs. [name] and [name] (Sripada et al., 2013).

Aim 2. To evaluate a sustained 6-week adjunctive DHEA treatment compared to PBO on PTSD symptoms severity (CAPS-5), co-occurring depression (BDI), and other secondary outcome measures such as resilience (CD-RISC). Following randomization to acute DHEA administration or PBO the subject will continue to receive study drug for 6 weeks (for DHEA, fixed escalating doses: 100 mg per day in divided doses x 1 week, followed by 200 mg per day in divided doses x 1 week, followed by 400 mg per day in divided doses x 4 weeks).

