For fMRI analysis we will use FSL supplemented by BIRN tools for signal averaging, ROI analysis, and visualization of time series waveforms (Smith SM 2004). We use FreeSurfer for surface reconstruction and automatic segmentation. FMRIB Software Library (FSL) preprocessing will be used for motion correction, slice time correction, temporal and spatial filtering, and co-registration with the individual subject's high resolution anatomical image. A first level analysis will be performed on each run separately using a standard GLM approach with regressors determined by the task timing convolved with a delayed canonical hemodynamic response. The first level analyses from a subject will then combined in a fixed effects second level analysis. These second level analyses are then combined into between group third level analyses using a mixed effects model. The functional MRI data will be analyzed by comparing whole brain voxelwise neural activity (BOLD) associated with cognitive processing between pre- and post-treatment, between active and placebo arms, between-face types (e.g. angry, fearful, neutral), and between-task conditions (e.g. gender, indoor/outdoor, like/dislike), which is neurosteroid relevant (Sripada et al 2013a, Sripada et al 2013b). [name] was the

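### The plan sets no independence rule for the functional ROIs used to infer treatment response and leaves unclear what the group-difference clusters do in the connectivity analysis, so circular inference is permitted and the hippocampal half of the primary endpoint may be tested only conditionally

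*Combined protocol and SAP*

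**What the plan says.** All of this is in the combined protocol and SAP. The Design section declares the endpoint: "The primary outcome measure will be functional connectivity between amygdala-hippocampus assessed using fMRI based SEAT Paradigm as a target engagement endpoint".

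The fMRI paragraphs of Data Analysis and Statistical Considerations begin with whole-brain voxelwise comparisons of activity "between pre- and post-treatment, between active and placebo arms, between-face types (e.g. angry, fearful, neutral), and between-task conditions". They continue: "Subsequent testing with functionally defined ROIs will be used to make statistical inferences about treatment response". The same ROIs are to be correlated with cognitive change, CAPS-5 and neurosteroid levels. The defining contrast and scan session are not given, and there is no hold-out, independent localiser or orthogonality rule.

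The next paragraph describes a drug by face-type by condition ANOVA on activation maps, reaction time and accuracy, with cluster-level correction. It then turns to connectivity: "The time series from significant clusters within regions of group difference will be used in a psychophysiological interaction (PPI) analysis". The following sentence reads: "Deconvolved time series in the anatomical right amygdala will be extracted for each subject and represent the first regressor in the PPI analysis". The description ends with "The regressor of interest will be the interaction between the time series of the seed region and the experimental condition".

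The hippocampus is not named anywhere in the analysis section. The tool that would define it anatomically is already planned: "We use FreeSurfer for surface reconstruction and automatic segmentation".

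**The concern.** There are three linked problems.

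1. If an ROI is drawn where the arms differ and the arms are then compared in that ROI on the same scans, the second test adds no evidence and its effect size is inflated by the selection. The plan permits this.
2. The two adjacent PPI sentences do not fit together. One sends group-difference clusters into the analysis; the next takes the physiological regressor from an anatomical region. If the amygdala is the seed, the natural remaining role for the clusters is as targets. The hippocampus would then enter only if its activation differed by arm, although connectivity can change without a change in activation.
3. ROIs are correlated with steroid levels that the treatment is expected to shift. A region that differs by arm can then correlate with steroids in the pooled sample without any association within either arm.

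At stake is the proof-of-concept claim. The choice of ROI and target could be made after seeing the arm maps, for the primary endpoint of a small trial.

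**Working it through.** The plan gives no power, effect size or error rate for the fMRI test, so there is no figure of its own to reproduce. From the documents: about 16 imaged participants per arm (32 in total, 30 df), alpha 0.05, two-tailed follow-up tests. Everything marked as assumed below is not in the documents.

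**Selection bound.** For two arms of 16, d = t × √(2/16).
- Assumed voxel threshold p<0.005: t(0.9975, 30) = 3.030, so |d| ≥ 3.030 × 0.3536 = 1.07.
- Assumed p<0.001: t(0.9995, 30) = 3.646, so |d| ≥ 3.646 × 0.3536 = 1.29.

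The bound carries over to the cluster average. In a cluster of one sign, every voxel's mean difference exceeds the same multiple of its pooled SD, and the pooled SD of an average cannot exceed the average of the pooled SDs. A cluster formed at p<0.05 or stricter must therefore be significant when its average is re-tested at 0.05.

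**Null simulation.** Assumed: 16 per arm, smooth 24×24 field, 1,500 runs per threshold, largest cluster taken, no cluster-size correction. For the PPI-type measure, rho is its assumed correlation with the activation estimate. Rates are rejections at 0.05. Rows for a selected cluster are conditional on a cluster existing.

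| | p<0.05 | p<0.01 | p<0.001 |
|---|---|---|---|
| Runs with any cluster | 99.5% | 78.6% | 21.1% |
| Same contrast, same data | 100% | 100% | 100% |
| Mean spurious \|d\| in that ROI | 1.14 | 1.21 | 1.47 |
| PPI-type measure, rho=0 | 5.8% | 4.1% | 6.6% |
| PPI-type measure, rho=0.3 | 12.8% | 12.8% | 18.0% |
| PPI-type measure, rho=0.6 | 41.3% | 41.4% | 59.0% |
| Selected ROI, independent data | 5.1% | 4.7% | 6.0% |
| ROI from an orthogonal contrast | 6.1% | 4.0% | 5.1% |
| Fixed anatomical ROI | 4.8% | 5.0% | 5.1% |

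Reuse of the same contrast fails completely. The PPI is distorted only as far as it correlates with activation. All three independent definitions stay near 5%. With no cluster (0.5%, 21% and 79% of null runs) there is no cluster ROI or target, but the amygdala seed remains.

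**Pooled correlation with steroids.** With equal arms, no within-arm association and arm differences d₁ (ROI) and d₂ (steroid):

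r = (d₁d₂/4) / √[(1 + d₁²/4)(1 + d₂²/4)]

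- d₁ = 1.07, assumed d₂ = 1.5: 0.401 / √(1.286 × 1.563) = 0.28.
- d₁ = 1.29, assumed d₂ = 3: 0.968 / √(1.416 × 3.25) = 0.45.

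By Fisher z at n = 32, √29 × atanh(r) is 1.57 and 2.62. The chance of exceeding 1.96 is about 35% and 74%. Nothing in the formula depends on how the ROI was drawn, so an anatomical ROI with a true arm difference behaves in the same way.

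**The case against.** The strongest reply is that the text never says the functional ROIs come from the arm contrast. Face-type and task-condition contrasts are listed too, and a region defined by a task effect across all participants is close to orthogonal to arm. That is right: circularity is permitted, not prescribed. Group difference is mentioned only for the PPI.

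A reader might infer that the PPI seed is taken from the clusters, so that without a significant cluster there is no seed and no primary analysis. The documents contradict this: "Deconvolved time series in the anatomical right amygdala will be extracted for each subject". The seed exists for everyone scanned. The cluster sentence says only that the time series are used in the PPI and never calls them the seed.

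A reader might also infer that the PPI result is built in. It is not. The regressor of interest is a seed-by-condition interaction, not the activation difference selected on, and the bias depends on a correlation that the documents do not give.

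The 100% figure is close to a tautology, and the plan does correct its maps at 0.05, so null clusters should be uncommon. This limits how often the problem arises. It does not make the re-test informative or remove the inflation once a cluster is found.

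Finally, the link between imaging and steroids is an exploratory aim. That lowers the stakes of the correlation point but does not change the arithmetic.

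**Conclusion.** The concern holds as a gap in the plan. ROI inference on treatment response has no stated defining contrast and no independence rule. If the arm contrast in the same scans is used, the ROI test is circular: the observed |d| is at least 1.07 at an assumed voxel threshold of p<0.005, and rejection is certain once a cluster exists. Correction of the maps controls how often a null cluster appears, not the size of the effect reported from it.

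For connectivity, the seed is secure, but the role of the clusters is unresolved and the hippocampus is absent from the analysis section. If the clusters are the targets, half of the declared endpoint is tested only after an arm difference in activation. Any resulting bias in the PPI ranges from none (4–7% null rejection at rho=0) through 13–18% at rho=0.3 to 41–59% at rho=0.6. Field size, smoothness, thresholds and rho are assumptions. The documents do not support the claim that the fMRI inference as a whole is circular by construction. Because the gap touches the primary endpoint, it should be closed before unblinding.

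**What to change.** In the fMRI paragraphs of Data Analysis and Statistical Considerations:

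- Remove the sentence that takes PPI time series from clusters of group difference, or label that analysis descriptive.
- Keep the anatomical right amygdala as the seed. Add a hippocampus target defined anatomically from the planned FreeSurfer segmentation, with laterality fixed before unblinding.
- State that the amygdala–hippocampus PPI estimate is computed for every scanned participant whatever the activation result, and is compared between arms.
- For inference on treatment response, use ROIs defined anatomically, by a contrast orthogonal to arm, or in independent data. Report ROIs found from the arm contrast as descriptive only.
- Estimate ROI correlations with neurosteroids and CAPS-5 within arm or adjusted for arm. An anatomical ROI alone does not remove an arm-driven pooled correlation.

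The cost is wording. The segmentation is already planned, and no further scans, data or participants are needed.

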### Purpose

This is a parallel-group, double-blind, placebo (PBO)-controlled, randomized Phase 2 pilot study using adjunctive dehydroxyepiandrosterone [DHEA (400 mg)] will be evaluated to establish Proof of Concept (POC) for this agent in Veterans with PTSD.

Our first objective is POC target engagement to evaluate a one-time adjunctive oral dose of DHEA (400 mg) relative to PBO on the neuronal circuitry of fear-anxiety-emotion connectivity. This will be achieved by comparing pre- to post-treatment changes in amygdala-hippocampal functional connectivity to DHEA and PBO during fMRI activation. We hypothesize that compared with PBO, DHEA will increase task-associated fMRI functional connectivity between the amygdala and hippocampus (primary outcome).

Our second objective is to determine if an 8-week treatment with adjunctive DHEA is superior to PBO in reducing symptoms of PTSD (CAPS-5) and depression (BDI) in OEF/OIF/OND Veterans, and enhancing resilience (CD-RISC). We hypothesize that 400mg DHEA will result in reduced PTSD and depression symptom severity relative to PBO, as determined by a pre- to post-treatment decrease in CAPS-5 and BDI scores, respectively, with enhancement in resilience scores using the CD-RISC at 6-weeks.

Our third objective is to evaluate the impact of DHEA relative to PBO on serum neurosteroid levels in OEF/OIF/OND Veterans with PTSD. We hypothesize that DHEA will result in a statistically-significant increase in serum neurosteroid levels (DHEA, DHEAS, androsterone) relative to PBO, as determined by pre- to post-treatment reductions in PTSD symptoms severity. This association will be evaluated by correlating neurosteroid levels with PTSD, depression, and resilience scores over 6 weeks of treatment.

Our exploratory objective is to determine preliminary evidence for an association of fMRI and myelin integrity measures of fear-anxiety-emotion circuits with serum neurosteroid levels and treatment response to DHEA. Changes in myelin integrity following DHEA treatment will be evaluated using novel susceptibility diffusion imaging [STI]), as DHEA impacts myelination in preclinical rodent models. We will also determine if serum neurosteroid levels are correlated with myelin integrity on STI. We hypothesize that fMRI and myelin integrity of fear-anxiety circuits will correlate with serum neurosteroids and treatment response.

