## PROTOCOL

Neurosteroids as Novel Therapeutic Agents for PTSD in OEF/OIF/OND Veterans  
PI: [name], PhD

PBO on neural circuits related to fear-anxiety-emotional regulation. We will determine potential fear-anxiety circuit target engagement following one-time oral adjunctive dose of DHEA (400 mg) using a same-day fMRI paradigm (the SEAT procedure, see below) to assess derived functional connectivity measures between the amygdala and the hippocampus as compared to PBO (primary outcome). Further, we will also determine if fMRI and serum neurosteroids (DHEA, DHEAS, androsterone, and/or other neurosteroids) may be candidate biomarkers of PTSD symptoms (CAPS-5) that predict therapeutic response to a DHEA intervention (secondary outcomes). The proposed set of studies will enable us to investigate these neurosteroids as novel pharmacological interventions for PTSD, and to identify biomarkers of therapeutic response in PTSD. Finally, as an exploratory goal, the current study will determine if treatment with DHEA impacts myelin integrity (as assessed by STI), and if peripheral neurosteroid levels are potentially associated with myelin content, other neuroimaging parameters, or therapeutic response.

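### The declared primary endpoint is amygdala-hippocampus connectivity, but the analyses labelled primary use activation, reaction time and accuracy, and no complete connectivity test is written

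*Combined protocol and SAP*

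**What the plan says.** **Declared endpoint.** Design, Aim 1, states: "The primary outcome measure will be functional connectivity between amygdala-hippocampus assessed using fMRI based SEAT Paradigm". The first objective under Purpose and the Study Interventions section name the same outcome, compared with placebo. Purpose describes the comparison as "comparing pre- to post-treatment changes in amygdala-hippocampal functional connectivity to DHEA and PBO during fMRI activation".

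**Stated analysis.** In Data Analysis and Statistical Considerations, the paragraph on primary outcomes opens: "Primary outcome analyses will be based on maps of activation, reaction time, and on-line accuracy judgments". The model is a 2 (drug) x 3 (face type) x 3 (task condition) repeated-measures ANOVA, examined for main effects and interactions.

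**Connectivity.** The same paragraph ends with a PPI analysis. One sentence on its input reads: "The time series from significant clusters within regions of group difference will be used in a psychophysiological interaction (PPI) analysis". The next reads: "Deconvolved time series in the anatomical right amygdala will be extracted for each subject and represent the first regressor in the PPI analysis". The regressor of interest is the interaction of the seed time series with the experimental condition, which is labelled only as emotion processing.

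**Scans.** Design, Aim 1, places imaging two hours after the dose. The Schedule of Events marks MRI at Weeks 2 and 8 only. The payments section counts two MRIs.

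**The concern.** The endpoint on which proof of concept rests and the analysis labelled primary are different things. Someone following the Data Analysis section could report a drug effect on activation or reaction time as the primary result without having tested amygdala-hippocampus connectivity between arms.

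The PPI could supply that test, but the items that define it are open: target region, task contrast, arm comparison and scan. The plan does not say they will be fixed before unblinding. With about 16 to 20 participants per arm, those choices can decide whether target engagement is claimed. The change score described under Purpose adds a further conflict, because no listed scan precedes the randomised dose.

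**Working it through.** **1. Endpoint against analysis.**
- Purpose, Design and Study Interventions: amygdala-hippocampus connectivity, DHEA versus placebo.
- Data Analysis, primary outcome paragraph: activation maps, reaction time, accuracy.
- The hippocampus is not named anywhere in the Data Analysis section.
- The ANOVA has 2^3 - 1 = 7 effects, of which 4 involve drug. None is singled out as primary.

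**2. What the PPI fixes and leaves open.**
- Given: right-amygdala seed; seed-by-condition regressor.
- Not given: hippocampal target; between-arm test of the PPI coefficient; which face or task contrast defines the psychological variable.
- The third-level between-group models earlier in the section are described for the task GLM, and the arm comparison stated there is of voxelwise BOLD activity. Extending them to the PPI is an inference.
- The two input sentences, one on clusters of group difference and one on the anatomical amygdala, are unclear together.

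**3. Number and timing of scans.**
- Plan's own figure: 5 visits x $75 + 2 MRIs x $100 = $375 + $200 = $575, as the payments section states. A third, pre-dose MRI would give $675.
- This agrees with the schedule (Weeks 2 and 8) and with the scan occasions in the SEAT description and the Exploratory Aim.
- Both scans follow randomised dosing. The only computable change, Week 8 minus Week 2, is not an acute change from baseline.
- A between-arm comparison on the Week 2 scan can be computed, and the wording in Design and Study Interventions fits it.

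**4. Size of the problem if the contrast stays open.** The documents give no effect size or correlation, so these are assumptions. Per-arm n is 16 (Exploratory Aim minimum) to 20 (all 40 scanned).

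*No correction, all contrasts null.* For k independent contrasts the chance of at least one false positive is 1 - 0.95^k: 1 - 0.95^3 = 14.3% and 1 - 0.95^9 = 37.0%. Nine is 3 faces x 3 conditions. Simulated two-sample t-tests with equal correlation 0.7 between contrasts give 11% (k = 3) and 21% (k = 9). The ranges are therefore 11-14% and 21-37%, almost identical at 16 and 20 per arm.

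*Bonferroni instead.* Power for one given contrast at d = 0.8, noncentral t, two-sided:

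| Per-test alpha | 16 per arm | 20 per arm |
|---|---|---|
| 0.05 (one named contrast) | 59% | 69% |
| 0.05/3 | 41% | 52% |
| 0.05/9 | 26% | 36% |

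Naming one contrast in advance avoids both the inflated error and the loss of power.

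**The case against.** The best defence is that connectivity has not been forgotten. The PPI is a connectivity method, it sits in the paragraph on primary outcome analyses, and its seed is the amygdala. The section says it is organised around the study hypotheses, and the connectivity hypothesis is stated by arm. This stands in part: the fair description is that a connectivity analysis is present but incomplete, under a lead sentence that names other variables. It does not supply the target, the arm test or the contrast.

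Several stronger readings are tempting, and the documents do not support them:
- **That the PPI runs only where activation differs between arms.** The cluster sentence can be read that way, but the seed sentence is unconditional, and nothing says the PPI is skipped if no cluster differs.
- **That the sentence on functionally defined regions, "Subsequent testing with functionally defined ROIs will be used to make statistical inferences about treatment response", is a further contradiction.** It precedes the primary outcome paragraph, and a functional region may lie inside the amygdala or hippocampus.
- **That no acute comparison is possible.** Only the change score is ruled out. Design and Study Interventions describe a post-dose comparison with placebo, and the ANOVA has no time factor.
- **That 37% is the expected error rate.** The plan promises correction for follow-up t-tests, activation maps and clusters within regions of interest, though not expressly for the PPI. The emotion-processing label also suggests fewer than nine candidates.

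**Conclusion.** The plan is wrong as written on this point and must be changed before unblinding. Following the Data Analysis section puts a different endpoint in the primary slot, and the only connectivity analysis is not specified well enough to be the primary test. The acute change described under Purpose cannot be computed from the two listed scans.

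The mismatch and the scan count come directly from the text and need no assumption. The error and power ranges in the working are illustrations under assumed effect size and correlation. The uncorrected rates are the upper end.

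A reader might also take the 59-69% power at d = 0.8 for a single named test as a measure of this defect. It is not: it follows from the sample size and is the same after the fix. What the defect can cost is the drop from that level, or the inflated error if no correction is made.

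**What to change.** **Data Analysis, primary outcome paragraph.** Name one primary test: DHEA versus placebo, two-sided 0.05, on each participant's PPI coefficient from the stated right-amygdala seed to an anatomically defined hippocampus, on the Week 2 post-dose scan. Say that it is run whatever the activation results show. Before unblinding, the sponsor fixes and records the hippocampal side (left, right or both), one task contrast, and the analysis set (randomised participants with a usable Week 2 scan). Activation, reaction time, accuracy and cluster-driven PPI become secondary or exploratory.

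**Purpose.** Reword the first objective as the post-dose arm comparison.

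**Data Analysis, fMRI paragraph.** State that any Week 8 versus Week 2 comparison is not the acute primary endpoint.

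**Cost.** Text changes and the sponsor decisions above; no new data, since the seed, the FreeSurfer segmentation and the Week 2 scan are already planned. The downsides are that activation, reaction time and accuracy lose primary status, and the post-dose comparison has no baseline scan to adjust for.

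Keeping an acute change score instead would need a pre-dose MRI for each participant: 32 x $100 = $3,200 to 40 x $100 = $4,000 in payments, plus scanner time that the documents do not cost.

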### Data Analysis and Statistical Considerations

The analysis plan is organized around the study's hypotheses using a variety of statistical techniques. Univariate summary statistics, including means, medians, rates, proportions, and variances, will be calculated as appropriate for all variables. In addition to statistics, outcome measures will be examined graphically to assist in determining distributional form as a precursor to model selection. Preliminary bivariate analyses by treatment condition will use standard Chi-square procedures for categorical outcomes; continuous outcomes meeting distribution requirements will be tested using Student's t-test, whereas data not meeting distributional requirements will be analyzed by nonparametric (e.g., Kruskal-Wallis) procedures. Differences between covariates will be tested at baseline to assess randomization. Putative covariates with significant asymmetry between groups will be considered for inclusion in subsequent modeling and testing (However, see Miller & Chapman, 2001). Inference for all analyses will be evaluated relative to  $p=0.05$  within a given hypothesis.

Analysis of primary outcomes in the Shifted-Attention Emotion Appraisal (SEAT) Paradigm will present compound stimuli that include both emotional faces (e.g. sad, happy, angry) and neutral scenes (Sripada et al 2014). In three different conditions, participants will be asked to respond to three different questions: (1) 'Gender': Whether the face in the foreground is male or female; (2) 'Inside/Outside': Whether the scene in the background is indoors or outdoors; or (3) 'Like/Dislike': Whether the face in the foreground is liked or disliked. This allows multiple components of cognition to be probed including (1) implicit emotional processing, (2) attentional modulation, and (3) cognitive modulation of emotion. Item-specific memory will be tested first using yes/no recognition judgments. The conjunctive memory test will require participants to make "match" (previously viewed faces and buildings presented in a combinations seen during encoding) or "mismatch" (items in combinations not previously seen together) judgments.

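### No stated correction or hierarchy spans the 12 drug terms of the ANOVAs labelled primary; testing each at 0.05 would give at least one false drug effect with probability about 0.30 to 0.46 (assumed outcome correlations 0.9 down to 0)

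*Combined protocol and SAP*

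**What the plan says.** All the analysis text is in Data Analysis and Statistical Considerations.

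- **General level.** "Inference for all analyses will be evaluated relative to" p = 0.05, applied inside each hypothesis. The section does not say whether that level is per test or for the hypothesis as a whole.
- **Analyses labelled primary.** "Primary outcome analyses will be based on maps of activation, reaction time, and on-line accuracy judgments", using a drug (2) by face type (3) by task condition (3) "repeated-measures ANOVA for main effects and interactions". No drug term is singled out and no order of testing is given.
- **Follow-up tests.** Two-tailed t-tests with "significance threshold at 0.05 with correction for multiple comparisons"; the method is not named.
- **Maps.** Three corrections are described: "Correction for the family-wise error rate will be based upon the Gaussian random field (GRF) theory that is implemented in FSL"; "second-level random-effects analyses using SPM8 and corrected for multiple comparisons"; and an AlphaSim cluster threshold "corrected for multiple comparisons within ROIs".
- **Other aims.** Hochberg's method is stated for Aim 2, and the paragraph on secondary measures ends by promising adjustment of its results. Neither statement refers to the Aim 1 ANOVAs.

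Elsewhere, Purpose, Design (Aim 1) and Study Interventions each name a single primary outcome: amygdala-hippocampus functional connectivity. It is not one of the three ANOVA measures. The analysis section comes to connectivity only afterwards, through the psychophysiological interaction (PPI) analysis.

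**The concern.** Four terms in each ANOVA contain drug: the main effect, drug x face, drug x condition and drug x face x condition. With three measures there are 12 omnibus drug tests under the primary label. Correcting the t-tests that follow a significant F-test does not limit how often an F-test is falsely significant. Correcting a map over its voxels or clusters does not deal with there being four such maps, or with the two behavioural measures beside them.

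The plan therefore describes multiplicity control for its secondary tests but none spanning the set of tests it calls primary. Nor does it say in advance which term would show a drug effect. Different terms could support different conclusions, and the choice among them could be made after the results are seen.

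**Working it through.** **Inputs from the documents.** Level 0.05; three measures; a 2 x 3 x 3 design with drug between subjects and face and condition within subjects; 32 analysed, about 16 per group.

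**Assumptions, not in the documents.** Each omnibus drug term is tested at 0.05. Each map term counts as one test held at 0.05 after voxel correction. Any significant drug term counts as a positive. The correlation rho between measures runs from 0 to 0.99.

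**Step 1: the plan's own figure.** In a null simulation (20,000 trials per setting, 16 per arm, sphericity holding), each drug F-test rejected in 0.047 to 0.054 of trials. The 0.05 is thus reproduced as a per-test level.

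**Step 2: independent tests.** The chance of at least one false positive in k tests is 1 - 0.95^k.

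- One measure, k = 4: 1 - 0.95^4 = 0.185
- Two behavioural measures only, k = 8: 1 - 0.95^8 = 0.337
- Map correction holding all four map terms jointly at 0.05, equivalent to k = 1 + 8 = 9: 1 - 0.95^9 = 0.370
- Three measures, k = 12: 1 - 0.95^12 = 0.460

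**Step 3: correlated measures.** The same simulation, counting trials with any drug term at p < 0.05:

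| rho | 12 terms, three measures | 8 terms, two behavioural measures |
|---|---|---|
| 0 | 0.458 | 0.336 |
| 0.3 | 0.441 | 0.329 |
| 0.5 | 0.419 | 0.316 |
| 0.7 | 0.384 | 0.305 |
| 0.8 | 0.351 | 0.286 |
| 0.9 | 0.302 | 0.258 |
| 0.99 | 0.223 | 0.210 |

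One measure alone gave 0.182 to 0.188. With 20 per arm and rho = 0.5 the 12-term figure was again 0.419, so sample size is not the driver.

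**Step 4: sphericity.** With AR(1) correlation of 0.8 across the nine cells and no sphericity correction, the 12-term rate was 0.486 (rho 0), 0.443 (rho 0.5) and 0.386 (rho 0.7).

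**Step 5: the remedy.** Bonferroni over 12 terms uses 0.05 / 12 = 0.00417 each, and 1 - (1 - 0.00417)^12 = 0.049 under independence. When no drug effect exists, Holm makes a false rejection exactly when Bonferroni does, so the same rates apply. Simulated under sphericity: 0.048 (rho 0), 0.046 (rho 0.5), 0.039 (rho 0.8). With the AR(1) pattern and no sphericity correction: 0.073 (rho 0), 0.071 (rho 0.5), 0.063 (rho 0.7). The remedy therefore needs a sphericity correction too.

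**The case against.** Several points on the other side have force.

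- **The plan corrects more than the follow-up t-tests.** A reader might infer that only those tests are corrected. The documents do not support that, because the maps are corrected as well. What remains is that no correction is stated across terms or measures, and the map methods do not touch the reaction-time and accuracy F-tests.
- **Target engagement is defined elsewhere.** A reader might infer that it could be claimed from any of the 12 terms, even a three-way interaction in reaction time. Design (Aim 1) reserves target engagement for amygdala-hippocampus connectivity, and Purpose gives the expected direction. The figures above are therefore not the error rate of that endpoint. This stands in full. It does not remove the point, because the analysis section still labels the ANOVAs primary. That section also takes PPI input from significant clusters where groups differ, so a false drug cluster might carry forward; this route was not quantified.
- **The 0.05 per omnibus test is an inference.** The general statement could mean a level for the whole hypothesis. But then no procedure is given that would achieve it, so the text needs completing on either reading.
- **The size depends on assumptions.** It would be wrong to present 0.30 to 0.46 as a fixed property of the plan.
- **This is a pilot.** Formal control over supportive behavioural measures is partly a matter of preference. That limits the severity, but a proof-of-concept study still has to say which result counts.

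**Conclusion.** The point holds in a limited form. The ANOVAs labelled primary contain 12 drug terms, and the plan states neither a hierarchy nor a correction across the four terms or the three measures, while it does adjust its Aim 2 and secondary tests.

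Under the assumptions listed, the chance of at least one false drug effect is about 0.19 for one measure and about 0.30 to 0.46 across three, for correlations of 0.9 down to 0. Even at a correlation of 0.99 it is 0.22, more than four times 0.05. Those rates describe the set of analyses labelled primary, not the declared connectivity endpoint. The gap should be closed before analysis; it does not call the design into question.

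**What to change.** In the primary-outcome paragraph of Data Analysis and Statistical Considerations:

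1. State that the sole primary test is one pre-specified DHEA-versus-placebo contrast on amygdala-hippocampus connectivity at 0.05, matching Purpose, Design (Aim 1) and Study Interventions.
2. Relabel the activation, reaction-time and accuracy ANOVAs as supportive.
3. If any inference about drug is drawn from them, apply Holm at 0.05 across all 12 drug terms, entering map terms after voxel correction, with a sphericity correction such as Greenhouse-Geisser. Otherwise report them as estimates with confidence intervals.

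Naming one drug term per ANOVA and adjusting only the other nine would not be enough. The named term would still be tested on three measures, 1 - 0.95^3 = 0.143. With the rest held jointly at 0.05, the total under independence is 1 - 0.857 x 0.95 = about 0.19.

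The cost is wording only, with no new data. The downside is that an isolated interaction in one measure would no longer count by itself as evidence of a drug effect.
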